Immuno-nutrition supplements are high in energy and protein (similar to conventional ONS), but also contain a unique combination of nutrients (i.e., omega-3 fatty acids, L-arginine and nucleotides), each acting in a complementary way to suppress inflammation, while concomitantly enhancing immune function [21]. Immuno-nutrition supplements (specifically Oral Impact®, Nestle) have been mostly used in pre-surgical settings, and previous studies conducted in cancer populations have reported a decrease in post-operative infections and length of hospitalisation, underpinned by evidence of a decrease in systemic inflammation [22].

This will be the first study to explore the potential effect of an immuno-nutrition supplement (Oral Impact®, Nestle) to address systemic inflammation in people receiving haemodialysis. The findings of this pilot study will help to design a randomised controlled clinical trial investigating whether a treatment bundle of resistance exercise training and immuno-nutrition supplementation can improve skeletal muscle mass, other markers of nutritional status and quality of life in people on haemodialysis.

STUDY OBJECTIVES AND PURPOSE

PURPOSE

The purpose of the present study is to investigate the impact of an immuno-nutrition supplement on systemic inflammation in people receiving haemodialysis.

PRIMARY OBJECTIVE

To investigate whether provision of an immuno-nutrition supplement decreases systemic inflammatory status in people on haemodialysis.

SECONDARY OBJECTIVES

To investigate the effect of an immuno-nutrition supplement on biochemical blood variables, body composition, dietary intake, skin autofluorescence (SAF) and muscle strength in people on haemodialysis.

DETAILS OF PRODUCT(S)

Description

Oral Impact® is a powdered oral nutritional supplement that contains a unique combination of ingredients with immuno-modulating properties, namely omega-3 fatty acids, arginine and nucleotides, as well as soluble fibre.

Manufacture

Oral Impact® is manufactured by Nestlé Health Science, Reg. Trademark of Société des Produits Nestlé S.A. OIDC 001

Packaging and labelling

Oral Impact® comes in a box that contains 5 sachets x 74g. Please see Appendix 1 for images of packaging and labelling.

Storage, dispensing and return

Oral Impact® will be stored unopened in a locked room which should be cool, dry and away from light and humidity. Access to the room will be restricted to members of the research team.

Known Side Effects

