No known side effects. However, Oral Impact® is unsuitable for people with cow's milk protein allergy and those who are severely septic. Oral Impact® should not be mixed with medication and food.

STUDY DESIGN

This will be a single-centre, non-randomised, interventional pilot study where people on haemodialysis will receive an immuno-nutrition supplement (Oral Impact®, Nestle) for 6 weeks.

STUDY CONFIGURATION

Primary outcome

Change in C reactive protein (CRP), and pro- and anti-inflammatory cytokine levels (via multiplex plasma analysis) after 6 weeks of treatment with an immuno-nutrition supplement.

Secondary endpoints

Change after 6 weeks of treatment with an immuno-nutrition supplement in:

- Biochemical blood variables including haemoglobin, urea, creatinine, potassium, phosphate, calcium, sodium, albumin, total proteins, total cholesterol and triglycerides.
- Body composition assessed with bioelectrical impedance analysis and BMI.
- Dietary intake assessed with 3-day food diaries.
- Muscle strength assessed with handgrip strength (HGS).
- SAF levels.

Safety endpoints

- AEs that occur will be reported during the study.
- Participant reported tolerability of the immuno-nutrition supplement.
- Monitoring of pre-dialysis serum potassium levels.

STUDY MANAGEMENT

The Chief Investigator (CI) has overall responsibility for the study and shall oversee all study management. The study will be co-ordinated from the University of Nottingham campus at the Royal Derby Hospital. Data will be collected at the Renal Dialysis Unit of the Department of Renal Medicine at the Royal Derby Hospital (University Hospitals of Derby and Burton NHS Foundation Trust) and stored at the University of Nottingham.

The CI and Co-investigators are responsible for study planning, recruitment, consenting, data collection, handling and interpretation. The data custodian will be the CI, [name].

DURATION OF THE STUDY AND PARTICIPANT INVOLVEMENT

Participant recruitment will begin in January 2022 once all necessary approvals are in place, with an anticipated total recruitment and intervention delivery period of 3 months (i.e., end of March 2022). The study will end when the last participant completes their final study visit.

SELECTION AND WITHDRAWAL OF PARTICIPANTS

Recruitment

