Pre- and post-dialysis blood samples (10 mL) will be taken at baseline and 6 weeks of follow-up and centrifuged at 2000g for 20-min to obtain at least 2 mL of plasma which will be frozen and stored at -80°C for subsequent analysis of circulating systemic pro- and anti-inflammatory cytokines via the Luminex multiplex platform.

Handgrip strength (HGS) will be measured at baseline and 6 weeks of follow-up using the Takei 5401 handgrip digital dynamometer (Takei Scientific Instruments Co., Ltd., Tokyo, Japan) within the first hour of haemodialysis treatment. The highest value of 3 attempts in the non-fistula arm will be recorded as HGS.

Body composition will be assessed via bioelectrical impedance analysis (InBody 770, InBody, Leicester, UK) and BMI at baseline and 6 weeks of follow-up.

Skin autofluorescence (SAF) will be measured using a validated Autofluorescence Reader (AGE Reader, DiagnOptics, Groningen, The Netherlands) at baseline and 6 weeks of follow-up. For each participant, three measurements will be performed on the volar surface of the lower arm at ~10 cm below the elbow, ensuring that the area has normal skin without visible vessels, scars or other abnormalities. Only the non-fistula arm will be used, and readings will be undertaken within the first hour of haemodialysis treatment.

Criteria for terminating trial

In the event of major safety concerns, new information, or issues with study conduct (e.g., poor recruitment, loss of resources), termination of the study will be considered by the sponsor. In the event of study termination, unused study resources will be reallocated as appropriate.

TRANSPORT AND STORAGE OF THE TISSUES

Pre- and post-dialysis blood samples (10 mL) will be collected at intervals as described above and centrifuged. At least 2 mL of plasma will be stored at -80°C for future analysis at the University of Nottingham Centre of Metabolism, Ageing & Physiology (COMAP).

Samples and data will be stored in a linked anonymised format. Samples will be labelled using a combination of study reference, unique study identifier and cross referenced with location code numbers to permit accurate linkage to study data and the consent form.

The master database will be held by the CI in a password encrypted file.

Where participants do not agree to the future use of the samples, they will be destroyed in accordance with the Human Tissue Act, 2004.

LABORATORY ANALYSES

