Blood samples will be taken at the Renal Dialysis Unit and transferred to the local NHS laboratory (which is serviced and managed according to national UKAS standards and governance frameworks) at the Royal Derby Hospital for routine biochemistry and

haematology testing. These samples will be labelled according to NHS requirements. No DNA or RNA extraction will occur as part of this study.

STATISTICS

Statistical analyses will be performed using SPSS version 28.0. Data will be presented as mean \pm standard deviation, median (interquartile range), or percentages, as appropriate. To compare baseline versus final evaluations, a Wilcoxon test or paired t-test will be used in the case of dimensional variables, and McNemar test in the case of categorical variables. Intergroup comparisons will be performed using Mann-Whitney test or Student t-test for continuous variables and χ^2 test or Fisher's exact test for categorical variables. An alpha error of less than 0.05 will be judged to be significant. All data will be analysed on University of Nottingham computers and backed up regularly.

Sample size and justification

A formal power calculation is not appropriate for this pilot study design, and consequently, the sample size has been selected on a pragmatic basis. We will aim to recruit 15 participants in total.

Procedures for missing, unused and spurious data

All missing data will be explained. If a space on the Case Report Form (CRF) is left blank because the procedure was not done or a question was not asked, "N/D" will be recorded. If the item is not applicable to the individual case, "N/A" will be recorded. All entries will be printed legibly in black ink. If any error is made in data entry, to correct the error, a single straight line will be drawn through the incorrect entry and the correct data entered above it. All such changes will be initialled and dated. Errors will not be erased or altered by any other method. For clarification of illegible or uncertain entries, the clarification will be printed above the item, initialled and dated. Correction fluid will not be used.

Definition of populations analysed

The study will analyse the following populations:

- Safety set: All participants who underwent at least one study session.
- Full Analysis set: All participants, who participated in at least one study session and for whom at least one post-baseline assessment of the primary endpoint is available.

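### The primary outcome is CRP plus an unnamed cytokine panel, with no lead marker, primary sample or success rule, so the stated 0.05 does not define the error rate of the primary objective.

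*Combined protocol and SAP*

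**What the plan says.** The primary objective is a directional question: "To investigate whether provision of an immuno-nutrition supplement decreases systemic inflammatory status in people on haemodialysis". Under Study Configuration, the primary outcome that answers it is "Change in C reactive protein (CRP), and pro- and anti-inflammatory cytokine levels (via multiplex plasma analysis) after 6 weeks of treatment".

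The data collection section identifies the cytokine work only by its platform, the plasma being frozen "for subsequent analysis of circulating systemic pro- and anti-inflammatory cytokines via the Luminex multiplex platform". It gives no analyte list and no panel size. The same section has two draws per visit: "Pre- and post-dialysis blood samples (10 mL) will be taken at baseline and 6 weeks of follow-up". Neither draw is called primary. CRP comes separately, from routine bloods at baseline and 6 weeks.

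The Statistics section says: "To compare baseline versus final evaluations, a Wilcoxon test or paired t-test will be used in the case of dimensional variables". It then sets one threshold: "An alpha error of less than 0.05 will be judged to be significant". The synopsis repeats both. Neither place states a hierarchy, a multiplicity adjustment, a composite score or the sidedness of the tests.

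The Full Analysis set takes in participants "for whom at least one post-baseline assessment of the primary endpoint is available". It does not say whether CRP, one cytokine or all of them meets that condition.

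**The concern.** The objective makes one claim, but the outcome supplies several tests. With CRP and m cytokines there are at least 1 + m tests, or 1 + 2m if both plasma draws are analysed. Because the panel mixes pro- and anti-inflammatory cytokines, the favourable direction also differs between markers, and it is not stated.

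The marker, the sample and the pattern of results that count as a decrease can therefore be chosen after the results are known. A single chance marker could then support the primary claim. The protocol intends publication and says the findings will help design a randomised trial, so such a marker could carry into that design.

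The same gap reaches the analysis population. A participant with a 6-week CRP but no cytokine result is neither clearly inside nor clearly outside the Full Analysis set. With 15 participants and no replacement, each such decision counts.

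**Working it through.** **Inputs from the protocol.** n = 15; 0.05 per test; Wilcoxon or paired t-test; one CRP change per participant; up to two contrasts per cytokine.

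**Inputs assumed, because the protocol does not give them.** Panel size m = 2, 5 or 10; two-sided tests; no true change in any marker; normally distributed changes; correlation between markers; correlation between the pre- and post-dialysis changes of the same cytokine. For the favourable-only rates, each marker is oriented so that less inflammation is the favourable direction.

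**Step 1: the plan's own figure.** For one test, 1 - 0.95^1 = 0.05. The stated level is the error rate only if a single test decides the objective.

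**Step 2: any-marker reading, independent tests.** The number of tests is k = 1 + m × (1 or 2 samples). The chance of at least one two-sided p<0.05 is 1 - 0.95^k. For favourable changes only it is 1 - 0.975^k.

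- k = 3 (2 cytokines, one sample): 14.3%; favourable only 7.3%
- k = 11 (5 cytokines, both samples): 43.1%; favourable only 24.3%
- k = 21 (10 cytokines, both samples): 65.9%; favourable only 41.2%

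These are ceilings. They treat pre- and post-dialysis values of one cytokine in one person as independent, which is implausible.

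**Step 3: any-marker reading, correlated tests.** One-sample t-tests on simulated changes, n = 15, with at least 40,000 trials per scenario. Each cell gives any two-sided p<0.05, then favourable only.

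| Assumed panel | Correlation 0.5 between markers, 0.8 pre-post | Correlation 0.95 between markers, 0.97 pre-post |
|---|---|---|
| 2 cytokines, one sample | about 13%; 6% | 7.5%; 3.9% |
| 5 cytokines, both samples | about 29%; 15% | 10.5%; 5.3% |
| 10 cytokines, both samples | about 42%; 21% | 12.1%; 6.0% |

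Repeat runs agreed to within about one percentage point. Using the Wilcoxon test instead gives 7.6-12.8% at correlation 0.95. Since the objective is a decrease, the favourable-only figures are the closer match, and their nominal value is 2.5%.

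**Step 4: all-markers reading.** If every marker had to be significant, the two-sided rate is at most about 3% (2.9%, with 2 cytokines in one sample at correlation 0.95).

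**Step 5: after a fix.** One pre-named marker at 0.05 has an error rate of 5%. At n = 15 it has 80% power for a paired change of about 0.78 SD. For a named panel, the first Holm step tests at 0.05/k. With k = 6 independent tests the rate is 1 - (1 - 0.05/6)^6 = 4.9%, and it is lower when the markers are correlated. The change detectable with 80% power at that first step rises to about 1.03 SD (k = 6), 1.11 SD (k = 11) or 1.20 SD (k = 21).

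**The case against.** The strongest reply is that the protocol never says one significant marker is enough. It joins CRP and the cytokines with *and*. Read as a requirement on all markers, that gives an error rate below nominal. This stands: a reader might infer that the plan inflates its false-positive rate, but the text supports only that the rate is undefined. Inflation follows from an any-marker rule that the plan neither adopts nor excludes.

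Second, this is a pilot. The sample size is pragmatic, the protocol calls a power calculation inappropriate, and no go/no-go decision is tied to a p-value. This lowers the severity but does not remove the point. The plan sets a significance threshold, poses an efficacy-type objective and does not label its tests exploratory.

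Third, the size depends on assumptions. That also stands. The panel size is not given, and a reader who took the 66% ceiling as the expected rate would go beyond the documents.

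Fourth, the Full Analysis set ambiguity matters only when one of a participant's results is missing, because CRP and cytokines are both collected at baseline and 6 weeks. That is fair. It is a secondary consequence of the same gap.

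**Conclusion.** The point holds in this form: the primary outcome has no named panel, primary sample, lead marker, adjustment or success rule, so 0.05 does not define the error rate of the primary objective. It should be fixed. It is not fatal to a pilot.

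Under an any-marker reading with 2 to 10 cytokines, the rate is about 13-42% at moderate correlation and about 8-12% at correlation 0.95. For favourable changes only it is about 6-21% and 4-6%, against 2.5%. Under an all-markers reading it is at most about 3%. Panel size, correlations and two-sided testing are assumptions, so these figures show the range and do not estimate this trial's error rate.

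A reader might also infer that selecting participants on CRP above 5.0 mg/L adds to the false-positive rate for CRP. That is a separate question. It depends on whether the qualifying value also serves as baseline, which the protocol does not say, and it is not part of this conclusion.

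**What to change.** Before any cytokine data are seen, list the cytokines by name, with the favourable direction for each, and name one sample time for them. Then choose one of two routes.

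- **(a) Single primary marker.** Test one lead marker at 0.05. CRP is the natural candidate, being listed first and already recorded at baseline and 6 weeks, but the choice is the sponsor's. The cytokines become secondary, with Holm or false-discovery-rate adjusted p-values.
- **(b) Named primary panel.** Keep CRP and the listed cytokines together as primary, with Holm adjustment across the panel.

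Under either route, state that the primary objective and Full Analysis set membership are judged on that endpoint or panel. For (b), say which markers must have a post-baseline value.

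The cost is a protocol amendment, which may need ethics committee and R&D approval before use. The plasma is frozen for later assay, so there may still be time to specify this before cytokine results exist. Under (a), a signal seen only in cytokines becomes hypothesis-generating. Under (b), the change detectable at n = 15 grows with the size of the panel, which favours a short list.

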15 participants will be recruited from the Renal Dialysis Unit at the Royal Derby Hospital. Potential participants will be approached by the clinical care team (which may include members of the research team) with reference to the inclusion and exclusion criteria. Each eligible participant will be given a Participant Information Sheet (PIS) and a minimum of 24 hours to consider whether they wish to participate in the study. At this time, the PIS will be discussed with them, any questions answered, and informed consent will be obtained by one of the investigators if they are willing to enter the study.

It will be explained to the potential participant that entry into the study is entirely voluntary and that their treatment and care will not be affected by their decision. It will also be explained that they can withdraw at any time. In the event of their withdrawal, it will be explained that their data collected so far cannot be erased and we will seek consent to use the data in the final analyses where appropriate.

If needed, the hospital interpreter and translator services will be available to assist with discussion of the study, the PIS, consent form, and be available for the duration of the study if required. The consent form and PIS will not be available printed in other languages.

Eligibility criteria

Inclusion criteria:

- CRP level >5.0 mg/L.
- Age: ≥ 18 years (no upper age limit).
- At least three haemodialysis sessions per week for ≥ 3 hours using a biocompatible dialyser.
- Able to give informed consent.

Exclusion criteria:

- Treatment with drugs that cause immunosuppression.
- Non-English speakers or those with special communication needs.
- Pregnancy, breast feeding or intending pregnancy.
- Expected survival <6 months.
- Hospitalisation at the time of screening.
- Known intolerance or allergy to ONS (or isolated ingredients).
- Pre-dialysis serum potassium >5.0 mmol/L.
- Unable to provide informed consent.

Participant Withdrawal

Participants will be withdrawn from the study if they:

- Withdraw their consent at any time.
- Become pregnant.
- Receive a kidney transplant.
- Do not adhere to the intervention; defined as $<50\%$ of the provided immuno-nutrition supplement being consumed.

Participants do not have to provide a reason for withdrawal of consent. Participants will also be withdrawn if it is deemed unsafe or is found to be impossible to proceed in the opinion of the investigators.

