Participants will receive individualised (to patient needs and food preferences) dietetic advice formulated and delivered by an experienced renal dietitian under an honorary NHS research contract ([name]), who is a member of the research team and will be supervised by an NHS renal dietitian, aiming to achieve estimated nutritional requirements for people on haemodialysis (i.e., energy: 30-35 kcal/kg/day, and protein intake: 1.0-1.2 g/kg/day) [23]. Each dietetic advice provided to participants will also be reviewed by the NHS clinical renal dietitians who are members of the participants' usual clinical care team.

Consumption of the immuno-nutrition supplement will be supervised during haemodialysis sessions (thrice weekly) and self-reported (written and counting empty sachets) on non-dialysis days. Participants will receive precise oral instructions on how and when to take the supplement with close monitoring by the renal dietitian on the research team to encourage adherence to the intervention.

Three-day food diaries (i.e., one dialysis day, one non-dialysis day and one weekend day) will be completed by the participants at baseline, 3 and 6 weeks of follow-up, and will be analysed (Microdiet, Downlee Systems Ltd, UK) to assess compliance with the advice provided and to assess energy, protein and fat intake across the study period.

Data collection procedures

Hospital electronic medical records will be used to collect relevant baseline participant characteristics, including age, sex, ethnicity, time since dialysis initiation, dialysis adequacy,

current medication, presence of diabetes and history of cardiovascular disease. Information regarding educational level, occupation status, and history of smoking will be obtained by direct interview with the participants at the time of the baseline assessment. A blood sample will be taken weekly pre-dialysis after commencing the immuno-nutrition supplement to monitor serum potassium. Results from routine clinical blood tests will be recorded at baseline and 6 weeks of follow-up and will include haemoglobin, urea, creatinine, potassium, phosphate, calcium, sodium, albumin, total proteins, total cholesterol, triglycerides and CRP.

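### Baseline CRP is not required to differ from the CRP result that qualified the patient, so regression to the mean could produce a CRP fall in this uncontrolled comparison

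*Combined protocol and SAP*

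**What the plan says.** - **Entry.** Eligibility criteria require "CRP level >5.0 mg/L". The number of readings, how recent they must be, and any repeat test are not stated.
- **Outcome.** Primary outcome: "Change in C reactive protein (CRP), and pro- and anti-inflammatory cytokine levels (via multiplex plasma analysis) after 6 weeks of treatment".
- **Design.** Study design describes a "single-centre, non-randomised, interventional pilot study where people on haemodialysis will receive an immuno-nutrition supplement"; there is no comparison arm.
- **Test.** Statistics compares baseline with final values by a Wilcoxon or paired t-test, with significance judged at 0.05.
- **Baseline CRP.** Data collection procedures: "Results from routine clinical blood tests will be recorded at baseline and 6 weeks of follow-up and will include haemoglobin"; CRP closes the list that follows.
- **Cytokines.** These have their own draw: "Pre- and post-dialysis blood samples (10 mL) will be taken at baseline and 6 weeks of follow-up".
- **Order of events.** Under Recruitment, patients are approached against the eligibility criteria and then given the information sheet and at least 24 hours to decide. Informed consent bars study-specific procedures before consent. Study regimen goes from consent to daily supplementation.

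**The concern.** A group chosen because a fluctuating marker was above a cut-off will, on average, read lower the next time, whatever is done to it. The usual protections are a baseline reading that played no part in selection, or a control group that shares the effect. This study has no control group, and the plan does not secure the separate baseline.

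Reuse is a realistic possibility. Patients are identified against the criteria before consent, and nothing study-specific may be done before consent. The qualifying CRP is therefore likely to be a routine result, the same kind of source as the baseline CRP. An investigator could follow the plan exactly and enter one value for both.

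The primary objective asks whether the supplement lowers systemic inflammation. A fall due to selection would point in the hoped-for direction, and nothing in the design would expose it. It would affect this pilot's own conclusion and could affect the decision to proceed. It would not directly size the later randomised trial, whose named outcomes are muscle mass, nutritional markers and quality of life.

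**Working it through.** **No plan figure to reproduce.** The sample size of 15 is pragmatic, with no SD, effect size or power. From the documents: cut-off 5.0 mg/L, n = 15, alpha 0.05, paired test, no control. Everything else below is assumed, including a two-sided test.

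**Model.** ln CRP is normal with total SD 1.0: a stable person-level part (variance rho) plus a fluctuation (variance 1 − rho). Patients enter if the qualifying value exceeds 5. There is no treatment effect, and the week-6 fluctuation is independent. The baseline fluctuation correlates c with the qualifying one: c = 1 is reuse, c = 0 an independent fresh draw.

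Expected ln ratio (week 6 / baseline) = −c × (1 − rho) × φ(z) / (1 − Φ(z)), with z = ln 5 − ln(median).

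- Median 5: z = 0, φ/(1 − Φ) = 0.798. With rho 0.65 and c = 1: exp(−0.35 × 0.798) = 0.756.
- Median 8: z = −0.470, φ/(1 − Φ) = 0.525. With rho 0.65 and c = 1: exp(−0.35 × 0.525) = 0.832.

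**Qualifying value reused, no upper limit.** Rates are simulated for n = 15 on untransformed CRP, counting only significant falls (nominal 2.5%; 2.4% for the exact Wilcoxon).

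| Median (mg/L) | rho | No-effect ratio | Wilcoxon | Paired t |
|---|---|---|---|---|
| 5 | 0.5 | 0.67 | 20% | 13% |
| 5 | 0.65 | 0.76 | 14% | 10% |
| 5 | 0.8 | 0.85 | 9% | 6% |
| 8 | 0.5 | 0.77 | 10% | 6% |
| 8 | 0.65 | 0.83 | 8% | 5% |
| 8 | 0.8 | 0.90 | 6% | 4% |

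A wider assumed grid (median 3 to 8, SD 1.0 to 1.2, rho 0.4 to 0.8) gives a spurious fall in geometric-mean CRP of 10% to 54%, so the size is driven by the inputs.

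**With an upper limit on qualifying CRP.** Patients in hospital at screening are excluded, which may remove some very high values. For a cap, replace φ(z)/(1 − Φ(z)) by (φ(a) − φ(b))/(Φ(b) − Φ(a)), with a = ln(5/median) and b = ln(cap/median). All rows are for reuse with rho 0.65.

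| Median | Cap | Ratio | Wilcoxon false fall |
|---|---|---|---|
| 5 | 30 | 0.79 | 11% |
| 8 | 30 | 0.89 | 3.9% |
| 8 | 20 | 0.94 | 2.4% |
| 10 | 30 | 0.95 | 2.3% |
| 12 | 30 | 0.995 | 1.4% |

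The log-scale shift reverses once the median exceeds √(5 × cap): √150 = 12.2 mg/L for a cap of 30, and √100 = 10 mg/L for a cap of 20. On untransformed CRP the excess of false falls disappears before that point.

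**Fresh baseline (median 5, rho 0.65, no cap).**

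| c | Ratio | Wilcoxon false fall |
|---|---|---|
| 0 | 1.00 | 2.3% |
| 0.3 | 0.92 | 4.5% |
| 0.5 | 0.87 | 6.5% |
| 0.7 | 0.82 | 9.1% |
| 1 (reuse) | 0.76 | 14% |

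**Share with a fresh baseline at or below 5 mg/L (c = 0).** At median 5 this is arccos(rho)/π: 33 / 27 / 20% for rho 0.5 / 0.65 / 0.8. At median 8 the bivariate normal gives 22 / 18 / 13%. From 15 × 0.13 to 15 × 0.33, that is about 2 to 5 participants.

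**The case against.** **The plan may already intend a separate baseline.** It refers to screening and to a baseline assessment as different occasions. It puts the routine results on the same baseline and 6-week schedule as grip strength and the cytokine blood, and Laboratory analyses says "Blood samples will be taken at the Renal Dialysis Unit and transferred to the local NHS laboratory". The baseline diary, "Three-day food diaries (i.e., one dialysis day, one non-dialysis day and one weekend day) will be completed by the participants at baseline", may add days before the first sachet. The contrast between results being recorded and samples being taken (as in "A blood sample will be taken weekly pre-dialysis after commencing the immuno-nutrition supplement to monitor serum potassium") is thin evidence in a short protocol. This stands as far as it goes: a reader might infer that the plan reuses the qualifying value, and no sentence says so. Equally, no sentence dates the baseline CRP sample or bars reuse.

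**The direction is not guaranteed.** A reader might infer that reuse must produce a fall. That holds only without upper selection; the capped results show the excess vanishing at higher medians. The documents give neither a median nor an upper limit. This objection stands.

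**The size is easily overstated.** The 20% figure is the extreme cell of the first table, and dividing it by a one-tail 2.5% suggests an eightfold inflation. Against the plan's 0.05 it is about fourfold, and the paired t-test, equally allowed, gives 4 to 6% at median 8. This also stands.

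**It is a pilot.** An uncontrolled CRP change is weak causal evidence even with a fresh baseline. That lowers the severity. It does not remove the point, because the plan poses a directional efficacy question and judges it at 0.05.

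**Conclusion.** The concern holds in conditional form. The plan permits the qualifying CRP to serve as baseline, without requiring it. If that happens, and very high values are not also screened out, a CRP fall is expected with no treatment effect.

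The size cannot be derived from the documents. On the uncapped assumptions above, the no-effect ratio is 0.67 to 0.90 and the falsely significant fall rate 4 to 20%, against 2.5% nominal in that tail. With an upper cap and a higher median the excess can be nil.

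A reader might extend this to the whole primary outcome. The documents do not support that: cytokines have their own baseline sample and no entry threshold, so they are affected only as far as they track CRP.

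Severity is minor to moderate: a cheap improvement to a pilot.

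**What to change.** Add to Data collection procedures:

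> Baseline CRP will be measured on a new pre-dialysis sample drawn with the baseline cytokine sample, after consent and before the first sachet. The CRP result used for eligibility will not be used as, or averaged into, baseline. The baseline value will be analysed whatever its level, and both sample dates will be recorded.

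State residual regression to the mean and the lack of a control group as limitations when reporting.

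Leave the potassium eligibility and safety rules alone. A similar fresh-sample rule for potassium would leave undefined what to do when the new value exceeds 5.0 mmol/L in someone about to start a sachet containing 10 mmol of potassium a day.

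**Cost.** At most one extra tube and one CRP assay per participant, at a draw already planned; nothing if routine bloods are sent that day. Under the assumed inputs, about 2 to 5 of 15 participants would be analysed with a baseline CRP at or below 5 mg/L. The bias is only partly removed if the two samples fall close together.
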